As a preliminary step toward designing a future study to assess the clinical benefits of the Tele-TC platform as a training system, we herein propose to assess:

- If the system enables monitoring longitudinally of adherence, proficiency, and safety;

- If the system is acceptable and user-friendly for its intended use in the home setting;
- As an exploratory aim, if a 12-week training program using the Tele-TC platform leads to improvements in balance, physical activity, self-efficacy, health-related quality of life, and gait.

If this preliminary study leads to positive results, we will embark on a follow-up study to assess the potential clinical benefits of using the technology as part of a clinical intervention on balance, physical activity, self-efficacy, health-related quality of life, and gait.

II. SPECIFIC AIMS

The overall goal of the study is to test the delivery of a novel Tele-Tai Chi (TC) intervention in a single-arm feasibility study for community-dwelling TC-naïve older adults (N=30 total). We will assess feasibility and acceptability measures of the Tele-TC intervention and its specific components through both qualitative and quantitative feedback, as well as the systematic tracking of adherence data to inform future trials and potential clinical use of the Tele-TC system. We will also explore changes in clinically relevant outcome measures including physical activity, self-efficacy, quality of life, balance, gait, and evaluate changes in TC proficiency.

We will pursue the following specific aims:

Primary aims

Aim 1: *To evaluate the feasibility, acceptability, and safety of a novel home-based Tele-TC intervention by tracking recruitment, retention, adherence, and adverse events.*

Hypothesis 1: We will be able to recruit 30 older adults and limit withdrawals to 20% or less.

Hypothesis 2: Participants will complete >60% of recommended Tele-TC sessions.

Hypothesis 3: Protocols for assessing safety can be developed and reliably administered, and preliminary evidence will support Tele-TC can be delivered safely.

Exploratory aims

Aim 2: *To evaluate changes in the level of proficiency of TC during a 12-week simplified TC program using the Tele-TC platform at home.*

Hypothesis 1: We will be able to collect reliable data on TC proficiency during Tele-TC use by study participants.

Hypothesis 2: Proficiency scores will improve over 12 weeks of training using the Tele-TC program.

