1. Physicians and therapists may refer interested patients to the study (we will provide physicians and therapists with study flyers and brochure to inform clinicians of the study details).

2. Flyers posted in outpatient clinics, therapy gyms, and public spaces both inside and outside the hospital campus.
3. PowerPoint presentation to inform clinicians and prospective participant about the study.
4. Contacts at local senior and community centers.
5. Recruitment letters sent to patients within the Partners network who have previously expressed interest for participating in research studies.
6. Via letters to prospective subjects co-signed by their physician and study PI.
7. Via contacts with patients who have consented to be directly contacted in the Partners Research Patient Data Registry (RPDR) or RSVP for Health.
8. Via the Partners Clinical Trials (Rally) website.
9. Via newsletters or community boards such as the Osher Center for Integrative Medicine newsletter.

The study procedures will be carried out remotely using a Zoom Enterprise Partners account or in person in the Motion Analysis Lab (MAL). Prior to the first visit, we will perform a phone screening to determine eligibility of prospective study volunteers. Individuals will be informed that identifiable information may be recorded during the phone screening. If a subject is deemed eligible, identifiable information (e.g. name, contact info) will be collected, and an informed consent form will be emailed to subjects for review. Baseline testing at a future date will be scheduled.

Eligible subjects will undergo the informed consent process via phone or on Zoom Enterprise with a trained research assistant at the beginning of baseline testing visit. The subjects will be provided with a signed copy of the consent form. The subjects may decide to pause or terminate their participation in the study at any time during the study.

IV. SUBJECT ENROLLMENT

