We will monitor falls during the subject's participation in the intervention study. Falls will be defined as any event in which the participant unintentionally comes to rest on the ground or other lower level, not as a result of a major intrinsic event or an overwhelmingly external hazard. Falls will be systematically monitored in two ways. As part of our safety and adverse events (AE) monitoring, participants will be asked to complete a weekly REDcap adverse events survey about their TC practice and activities of daily living. Study staff will follow-up by phone with participants as necessary. During study visits #1b-#4, study personnel will inquire about and record characteristics and details of falls and other adverse events.

5. Feedback from the Subjects

During the last visit (visit #4), we will conduct a semi-structured qualitative interview to gather feedback from the subjects regarding the feasibility and acceptability of the study overall, and more specifically the usability of the Tele-TC platform. We will ask them to provide us with feedback regarding general characteristics of the platform, possible improvements of the system, and whether they would consider using the system on a daily basis at home. The qualitative interview will be audiorecorded. In addition, at the end of the study, we will use an adapted version of the System Usability Scale (SUS).

6. In Lab Assessments (Visits #1b and #4)

Subjects will be asked if they are willing to perform a lab testing at baseline and post-intervention visits (#1 and #4) in the Motion Analysis Laboratory (MAL) at Spaulding Rehabilitation Hospital (SRH). Lab visits will include the same battery of assessments utilized in the remote visits, as well as the Mini Balance Evaluation System (Mini BEST) Test. The lab visits will include instrumented monitoring of TC performance as well. The miniBEST is a shortened version of the Balance Evaluation System Test (BESTest). It is a 14-item test scored on a 3-level ordinal scale. It aims to target and identify different balance control systems. The sessions will be videotaped, and the miniBEST test may be instrumented.

7. Return of devices

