The subjects will be asked to return the devices (mobile devices, sensors, tablet stands) in a prepaid and addressed box by mail after the completion of the study. The final payment for the study (\$50) will be contingent on the return of the study equipment. Those that come into the lab for their final testing visit will be asked to return the devices in person.

VI. BIOSTATISTICAL ANALYSIS

The primary outcomes of the study are the retention and the protocol adherence during the study, and the System Usability Scale collected post-intervention.

The exploratory outcomes will include the following:

- The ease of use of the Tele-Tai Chi platform measure with the qualitative interview collected post intervention.
- The changes in outcomes collected at baseline and post-intervention: the Activities-specific Balance Confidence (ABC) scores, PROMIS 29 scores, the Physical Activity Scale for the Elderly (PASE), the Trail Making Test A/B scores, Self-Efficacy Exercise (SEE) scores, the Timed-Up-and-Go, the Timed-Up-and-Go dual task single leg stance, the Sit-to-Stand performance, the balance on both legs with feet shoulder-width apart, the balance on both legs with feet close to each other, the normalized-to-height stride length and stride time variability, the activity level, and the Mini-Balance Evaluation Systems Test (MiniBEST) collected only in individuals who are willing to be tested in the MAL
- The changes in The Tai Chi proficiency scores collected at baseline, 4 weeks, 8 weeks, and pos-intervention.

Descriptive statistics will be derived for all the above-described clinical assessment outcomes and correlations will be sought with the sensor-based estimates of the metrics of adherence, proficiency and safety derived using the previously developed algorithms. Exploratory statistical analyses will be performed to power future clinical studies aimed to test the relationship between the proposed metrics of adherence and proficiency and the clinical outcomes of the intervention. Whereas conclusive statistical analyses to explore such correlations are beyond the scope of the proposed project, the data collected in this pilot study are expected to provide justification for a future trial aimed to assess the efficacy of the Tele-TC Platform as a training system.

VII. RISKS AND DISCOMFORTS

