When - according to a rehabilitation specialist during in-person testing, or research staff during virtual testing - subjects are unable to safely perform the TC exercises that are part of the experimental procedures, the experiment will end. Subjects will be told why the experiment must stop and will be advised to seek medical care if appropriate.

Subjects will be told that the study procedures may be associated with discomfort due to wearing the sensors and by fatigue/muscle soreness. In case subjects experience discomfort or excessive fatigue, they will be free to remove the sensors and end their participation in the study.

Foreseeable Risks and Discomfort

Unintentional loss/disclosure of Protected Health Information may occur and is considered a minimal risk due to the security measures enforced at SRH. Confidential information will be kept in a locked filing cabinet, on REDcap, and on password-protected computers in the MAL.

VIII. POTENTIAL BENEFITS

Study participants are not expected to directly benefit from their participation, but it is possible that subjects will experience some positive impact on physical and mental health as a result of their performing TC exercises, as has been shown in prior TC studies. Information gained during the study is expected to contribute to the development of systems to facilitate the deployment of TC-based interventions.

IX. MONITORING AND QUALITY ASSURANCE

Because this study's procedures pose minimal risk to the subjects, bimonthly data and procedural reviews by the PI in consultation with study staff will be sufficient to identify and ameliorate any

potential safety issues. Any safety concerns about the equipment or testing protocol will be brought to the immediate attention of [name]. Study staff will conduct bimonthly audits to ensure compliance with regulatory requirements for study documentation.

Approval of protocol, informed consent procedures, and recruitment will be obtained from the IRB during annual reviews.

Adverse event reporting will be done according to Partners Human Research Policy. Remedial action to prevent reoccurrence of the event will be instituted prior to the resumption of study procedures.

Study staff will conduct quarterly audits to ensure compliance with regulatory standards for study documentation.

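### No usability rating or reason for stopping is specified for participants who use the platform and then withdraw, although the SUS is a primary outcome

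*Combined protocol and SAP*

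**What the plan says.** On the outcome and its timing, Section VI states: "The primary outcomes of the study are the retention and the protocol adherence during the study, and the System Usability Scale collected post-intervention". Section V.5 adds: "In addition, at the end of the study, we will use an adapted version of the System Usability Scale (SUS". For the interview, the same section says: "During the last visit (visit #4), we will conduct a semi-structured qualitative interview to gather feedback from the subjects". Its topics include whether the participant would use the system daily at home. Section VI likewise dates the interview after the intervention, and Section V.6 treats visit #4 as the post-intervention visit. The opening of Section V also lists an interview at visit #1. Its content is not described, and it takes place before the 12 weeks of home use.

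On leaving, Section III says: "The subjects may decide to pause or terminate their participation in the study at any time during the study". The Safety part of Section VII says: "In case subjects experience discomfort or excessive fatigue, they will be free to remove the sensors and end their participation in the study". Aim 1, Hypothesis 1 sets the expected limit: "We will be able to recruit 30 older adults and limit withdrawals to 20% or less".

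On contact between visits, Section V.4 says: "participants will be asked to complete a weekly REDcap adverse events survey about their TC practice and activities of daily living". Staff telephone as necessary. If staff stop the procedures on safety grounds, Section VII says: "Subjects will be told why the experiment must stop and will be advised to seek medical care if appropriate".

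**The concern.** The study asks whether the system is acceptable and user-friendly in the home (Section I). People who tried it and stopped are directly informative on that question. Section I counts the sensors as part of the system, and Section VII foresees discomfort from wearing them, so some reasons for leaving may be properties of the system being rated.

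Retention and adherence, also primary outcomes, count these people but do not record how they rated the system or why they left. A SUS taken only after the intervention would come from those willing to stay. It could not help separate losses due to the sensors, the app or the exercise burden from losses with unrelated causes. Ratings not requested at exit are hard to recover later. What is at stake is the interpretation of one primary outcome and the lessons for the next version of the system and the next trial.

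**Working it through.** **1. Is a rating or a reason for stopping specified for leavers?** The possible routes, taken in turn:
- SUS: post-intervention (VI) and at the end of the study (V.5). Neither section mentions withdrawn participants.
- Feedback interview: visit #4 (V.5). The visit #1 interview (V) comes before home use, so it cannot record experience of it.
- Weekly survey and telephone calls (V.4): for adverse events and falls, with calls as needed. No usability rating is mentioned. A reason may surface, but nothing says every leaver is asked.
- Safety stop (VII): staff tell the participant why; the participant is not asked for a rating.
- Other contacts: visits #2 and #3, live sessions with the instructor, the invitation to raise concerns at any time (VII), and return of devices (V.7). None is described as collecting a rating or a reason for stopping.

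**2. How many could be missing?** The plan's only relevant figures are N = 30 and the 20% limit: 0.20 x 30 = 6 withdrawals, and 30 - 6 = 24 with a post-intervention SUS.

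**3. Who is in scope?** Devices go out only after consent (V.1), so someone who leaves before any use has nothing to rate. Participants follow the platform at visit #1B (V.2), so most who leave after that visit would have used it at least once.

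**4. Possible size (illustration).** The documents do not give the scoring of the adapted SUS, its SD, or any difference between leavers and others. Assumed: a 0-100 scale, and leavers rating g = 0 to 40 points lower.

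Let c be those with a post-intervention SUS, with mean m, and u the leavers who used the platform, with mean m - g. The all-user mean is [c m + u(m - g)]/(c + u) = m - w g, where w = u/(c + u). The overstatement is w g. With no assumption on g, setting every leaver to 0 or to 100 gives a range 100w wide for the all-user mean.

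| c | u | w | Overstatement, g = 0 to 40 | Best/worst-case width |
|---|---|---|---|---|
| 24 | 6 | 6/30 = 0.200 | 0 to 8.0 | 20.0 |
| 24 | 4 | 4/28 = 0.143 | 0 to 5.7 | 14.3 |
| 24 | 3 | 3/27 = 0.111 | 0 to 4.4 | 11.1 |
| 24 | 0 | 0 | 0 | 0 |
| 27 | 3 | 3/30 = 0.100 | 0 to 4.0 | 10.0 |
| 27 | 2 | 2/29 = 0.069 | 0 to 2.8 | 6.9 |
| 21 | 9 | 9/30 = 0.300 (above the limit) | 0 to 12.0 | 30.0 |

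**5. Against sampling error.** The 95% half-width for 24 ratings is t(0.975, 23) x SD/sqrt(24) = 0.422 x SD, which is 4.2, 6.3 or 8.4 points for an assumed SD of 10, 15 or 20. The gap at which the overstatement equals this is the half-width divided by w:
- w = 6/30: about 21, 32 or 42 points.
- w = 4/28: about 30, 44 or 59 points.
- w = 3/30, with 27 ratings (0.396 x SD): about 40, 59 or 79 points.

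Within the hypothesised limit, then, the possible bias exceeds sampling error only if leavers differ greatly.

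**The case against.** The strongest reply is that the text is silent on leavers and does not exclude them. The SUS sentence is separate from the visit #4 interview sentence, and neither Section V.5 nor Section VI restricts the SUS to people who finished 12 weeks. A participant may pause or stop training and still answer the post-intervention survey. Figure 2, the weekly survey items and the interview guide are not shown, so an exit item there cannot be ruled out. This stands. A reader might infer that the SUS will cover completers only, or that no reason for leaving will ever be recorded; the documents support neither.

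It can also be said that the numerical effect is entirely assumed, that Section VI plans no test of the SUS and states no threshold, and that retention already shows how many ratings are missing. This stands too. A reader might infer that reported usability will be inflated, but nothing in the documents shows that leavers would rate the system lower.

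Finally, a rating after a few sessions and one after 12 weeks reflect different exposure, so an exit SUS supplements the 12-week figure and does not complete it. That is correct and shapes the remedy. None of these points supplies a specified rating or reason for stopping from people who used the platform and left.

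**Conclusion.** The point holds as a gap in specification and a cheap improvement. Followed as written, the plan is likely to yield a SUS only from those who reach the post-intervention assessment, and it does not say how the views of other platform users will be sought. The firm figure is coverage: 24 of 30 at the 20% limit, and fewer if more leave.

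The direction and size of any bias are unknown. The 0 to 8 points at 6/30 rests on the assumed scale, the assumed gap, and all six leavers having used the platform. If none had, the bias is zero. No decision rule is affected, and confidence is medium because relevant material is not shown.

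**What to change.** Offer the SUS, the home-use question and a short question on reasons for stopping by REDCap at visit #4 or at withdrawal, whichever comes first. Send them to everyone with at least one session in the platform's automatic log (Section V.3), and state whether the visit #1B session counts. Make the survey optional for leavers and record time on the platform when the rating is given.

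Keep the 12-week SUS as planned and show early-exit ratings separately. Report respondents out of all platform users, with a best/worst-case range for non-responders. If the end of the study was meant as each participant's own end, say so in Section V.5 and extend it explicitly to withdrawals. Also state what the visit #1 interview covers.

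The cost is an IRB-reviewed change to the protocol and consent, one more survey trigger in a system already in use, and a few minutes per leaver (six people at the 20% limit). Some leavers will not respond, so the gain will be partial, and the reported usability may be less favourable.

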PARTNERS HUMAN RESEARCH COMMITTEE

DETAILED PROTOCOL

PRINCIPAL/OVERALL INVESTIGATOR

[name]

PROTOCOL TITLE

A Mobile Tai Chi Platform for Fall Prevention in Older Adults – Phase II

FUNDING

NIH

VERSION DATE

8/6/2021

I. BACKGROUND AND SIGNIFICANCE

TC is a multi-component mind–body exercise that is growing in popularity worldwide, especially among older adults. TC integrates training in balance, flexibility, and neuromuscular coordination with a number of cognitive components including heightened body awareness, focused mental attention, and multi-tasking, which together may result in benefits to postural control, beyond conventional exercise ^{1,2}. Meta-analyses support that TC reduces falls by 20-45% ³. A recent Cochrane review concluded that TC is among the most effective available exercise options for fall prevention in ambulatory older adults ⁴. TC appears to reduce falls by positively impacting multiple fall-related risk factors including: lower extremity strength and flexibility, proprioception and postural awareness, neuromuscular coordination, executive function, and fear of falling ⁵.

While research is beginning to provide guidelines regarding targeted applications of TC-based therapies for specific medical conditions and populations, methodological challenges limit the conclusions that can be drawn from this research ⁶. One important challenge inherent in the study of multi-component mind-body interventions is objectively quantifying measures of adherence and proficiency. Because variability in proficiency of practice can significantly alter physiological responses to a training session, simple measures of class attendance or logged practice time are unlikely to capture practice components needed to objectively evaluate the impact of TC-based interventions on clinical outcomes of interest. The development of objective, non-invasive measures that can accurately record and verify practice of specific TC intervention components, along with measures of practice duration, would represent a significant advance in the field.

During phase I of the SBIR NIH grant, we developed algorithms based on information gathered from wearable sensors to estimate adherence, proficiency, and safety metrics. During the non-clinical stages of phase II, we developed a complete beta-version of the Tele-TC platform. The Tele-TC system consists of a set of 5 wearable sensors and an app installed on a commercially available tablet.

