When subjects first contact the study team, a member of the study team will provide them with a detailed description of the study over the phone or in person. If interested and deemed potentially eligible, a member of the study team will offer to send the informed consent form to the subject. Subjects will be encouraged to call study staff with any questions or concerns they might have prior to their first study visit. Consent will be obtained remotely using the eConsent process on REDcap by a trained research staff member designated by the Principal Investigator as adequately knowledgeable of the risks/benefits of the study and the vulnerability of the study population and capable to critically assess the subject's awareness of these factors. The subject will be encouraged to continue to ask questions and express concerns - if any - to study staff throughout their participation in the study. Enrollment will begin when it is clear that the subject thoroughly understands and e-signs the informed consent form. Testing will only take place once the informed consent form is signed.

V. STUDY PROCEDURES

The study procedures will be carried out remotely using a Zoom Enterprise Partners account or in person.

Eligible subjects will undergo the informed consent process in person, by phone or on Zoom Enterprise with a trained research assistant at the beginning of the baseline testing visit. Once consented, subjects will undergo baseline assessments (visit #1) in person or remotely using Zoom Enterprise and REDcap Survey. After baseline testing, subjects will participate in the Tele-TC intervention, with recommended training sessions at least three times a week, along with two or more supplementary one-on-one live sessions (lasting upwards to 45 minutes) with TC instructors. TC proficiency using wearable sensors will be assessed at visit #1 baseline, at two follow-up assessments (visit #2 and visit #3) at approximately 4 and 8 weeks, and at a final assessment (visit #4) at 12 weeks. A semi-structured qualitative interview will also be performed at visit #1 and #4.

[figure not shown]

Figure 2: Flow Chart of the study.

Below, we provide a detailed description of the study procedures.

1. Remote Screening and Informed Consent (Visit #1A)

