Study staff will use Zoom to communicate with subjects during these visits if done remotely. We hypothesize that data collected over 4 sequential visits will show that the sensor-based estimates of the metrics of adherence, proficiency, and safety developed in Phase I are sensitive to longitudinal changes that take place in response to the interventions. The performance of TC exercises will also be videorecorded and scored using the proficiency metric described in our preliminary studies section to provide a gold standard.

Subjects will be asked to don one Smart GeneActiv watch by ActivInsights* in their wrist to monitor activity during approximately a week after visits #1B and a week before visit #4.

We will ask the participants to send the GeneActiv back to the lab after wearing it. We will be sending another GeneActiv about two weeks before visit #4.

3. TC Training Sessions the Tele-TC Platform (12 weeks)

Study volunteers will participate in a 12-week simplified TC program that we have used in multiple prior clinical studies. In this pilot study, the intervention will be delivered via our platform-based application. All participants will be provided with a tablet with the Tele-TC software installed. The structured intervention, designed for older adults, emphasizes essential TC movements that are easily comprehensible and can be performed repetitively in a flowing manner. The protocol includes up to six core TC movements based on the traditional Cheng Man-Ch'ing's Yang-style short form. Additionally, a complementary set of traditional TC warm-up exercises that focus on loosening the physical body, incorporating mindfulness and imagery into movement, promoting overall relaxation, and coordinating breathing awareness are included. Chairs are used in the

protocol for a subset of seated warm-up exercises, as well as for stability and rest as needed. Participants will be asked to practice the protocol (45-60 min) at home for at least 3 days a week for 12 weeks. In addition to data on practice frequency, duration, protocol adherence and training proficiency being automatically collected through our platform, a weekly REDcap survey will be used to monitor adverse events. The TC program will also include 2 or more live instructional sessions via Zoom with a TC instructor.

4. Remote Monitoring of Falls and Other Adverse Events

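### Do adverse events and falls need adding to the Section VI outcome lists because primary Aim 1 relies on them?

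*Combined protocol and SAP*

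**What the plan says.** Section II (Specific Aims) sets one primary aim, covering feasibility, acceptability and safety, to be evaluated "by tracking recruitment, retention, adherence, and adverse events". Its third hypothesis concerns safety: "Protocols for assessing safety can be developed and reliably administered, and preliminary evidence will support Tele-TC can be delivered safely". It has no numeric criterion, whereas the first two hypotheses have limits of 20% for withdrawals and 60% for sessions completed.

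Section V says how the data arise. Under V.3, "a weekly REDcap survey will be used to monitor adverse events". Section V.4 gives a definition: "Falls will be defined as any event in which the participant unintentionally comes to rest on the ground or other lower level", with a qualification for major intrinsic events and external hazards. It also adds a second route, in which staff ask about falls and other adverse events at visits 1b to 4. Section IX provides for bimonthly review by the principal investigator and for reporting of adverse events under institutional policy.

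Section VI then states: "The primary outcomes of the study are the retention and the protocol adherence during the study, and the System Usability Scale collected post-intervention". The exploratory list covers ease of use from the interview, changes in clinical and activity measures, and Tai Chi proficiency. Safety appears there once, in "sensor-based estimates of the metrics of adherence, proficiency and safety derived using the previously developed algorithms". Section I traces these metrics to Phase I, which developed "algorithms based on information gathered from wearable sensors to estimate adherence, proficiency, and safety metrics".

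**The concern.** The analysis section of a protocol should give every primary aim a measure. Here adverse events are one of four measures named for Aim 1, and they are missing from both Section VI lists. The planned descriptive statistics are for the clinical assessment outcomes listed just before, so that sentence does not reach adverse events or falls either.

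The wording adds a risk of misreading. Someone who opened only Section VI could take the sensor metric to be the safety outcome of the study. Neither half of Hypothesis 3 (reliable administration of the safety procedures, and safe delivery) has a stated measure.

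The subject matter gives the point some weight. The platform is meant for fall prevention, participants are 60 to 85 years old, and they practise at home. If falls and adverse events went unreported, or if an absence of events were presented without its uncertainty, a future trial would be planned on a weak safety statement.

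**Working it through.** No stated figure depends on this point, so there is no plan figure to reproduce. The check is a comparison of sections, followed by the arithmetic on what a safety summary could show.

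**1. Aim 1 measures against Section VI**

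| Aim 1 measure (Section II) | Named in Section VI? | Provided for elsewhere? |
|---|---|---|
| Recruitment | No | Hypothesis 1: target of 30 |
| Retention | Yes, primary | Hypothesis 1: withdrawals at most 20% |
| Adherence | Yes, primary | Hypothesis 2: over 60% of sessions |
| Adverse events, including falls | No | V.3 weekly survey; V.4 fall definition and visit questions; IX review and reporting |

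Two of the four measures are absent from Section VI. Recruitment is absent in the same way, and nobody would doubt that the number recruited will be reported. This suggests that Section VI was not written as a complete inventory of Aim 1.

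**2. What an analyst has to hand**

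- An instruction to track adverse events under the primary aim (Section II).
- Two collection routes and a definition of a fall (V.3 and V.4).
- A definition of enrolment: "Enrollment will begin when it is clear that the subject thoroughly understands and e-signs the informed consent form" (Section IV).
- Oversight and reporting (Section IX).

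Only the format of the table is unstated.

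**3. What the table could show**

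Inputs: n = 30 (Sections II and III); n = 24 if the tolerated 20% withdraw, since 30 × (1 − 0.20) = 24. The event counts are assumed for illustration, because the documents give no rates. For zero affected participants the exact two-sided 95% upper limit is 1 − 0.025^(1/n). Other intervals are Clopper-Pearson.

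| Affected / n | Proportion | Exact 95% CI |
|---|---|---|
| 0/30 | 0% | 0% to 1 − 0.025^(1/30) = 11.6% |
| 1/30 | 3.3% | 0.1% to 17.2% |
| 2/30 | 6.7% | 0.8% to 22.1% |
| 3/30 | 10.0% | 2.1% to 26.5% |
| 0/24 | 0% | 0% to 1 − 0.025^(1/24) = 14.2% |

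These limits depend on n and the count alone. Listing adverse events in Section VI would leave them unchanged, so they describe the precision of a small study and do not measure the omission.

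**4. Would one added line settle the matter?**

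A line naming adverse events and falls over all consented participants would still leave recruitment unlisted, so the lists would not match Aim 1. Consent comes before testing and before devices are supplied (Sections IV and V.1), and Section VII uses clinical tests to judge who can safely do the exercises. Some enrolled people may therefore never use Tele-TC. If 6 of 30 never started (an assumption), 3 affected would be 3/30 = 10.0% of those enrolled but 3/24 = 12.5% of those exposed. The weekly survey also covers both practice and daily living (V.4), so a single pooled count would not isolate events during practice. Such choices are better made with the data layout in view than fixed by a short insertion.

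**The case for a change.** The strongest case for a change is that the primary list is worded as closed, Aim 1 is primary, and no other sentence assigns adverse events or falls to an analysis. Section IX is oversight, not analysis. The exploratory list is introduced in a way that may be open-ended, but that does not help a primary aim. The sensor metric shares the word safety and could be mistaken for the outcome. An alignment edit would cost a line or two and a small table, with no new visit or participant, and a stated denominator with an interval would discourage reading no events as no risk.

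The textual part of this stands in full: the omission is there, and tidier drafting would have avoided it. What does not stand is the step from omission to consequence. Collection, monitoring and reporting are unaffected. Hypothesis 3 sets no threshold, so no conclusion turns on how the table is laid out. The sensor metric is described as sensor-based where it appears, and Aim 1 names adverse events, so the confusion requires reading Section VI in isolation. Reporting uncertainty with a zero count is good practice at the writing stage and does not depend on the outcome list.

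**Conclusion.** The observation is correct and no change to the plan follows. Section VI omits adverse events and falls, but the protocol elsewhere directs that they be tracked, defines falls, provides two collection routes, and arranges review and reporting. What remains is presentational detail that analysts fill sensibly.

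The size of the effect on the plan is nil: no sample size, threshold, estimate or decision rule moves. Any safety statement from this study is descriptive, with an upper limit of 11.6% for zero affected among 30, or 14.2% among 24, however Section VI is worded.

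This rests on two assumptions: that the report will tabulate adverse events and falls because Aim 1 calls for them, and that it will not present the sensor metric in their place. Neither is guaranteed by Section VI, but both follow from an ordinary reading of the whole protocol.
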